10.2 STOPPING RULES FOR EFFICACY

When 17 evaluable patients have been treated with at least one DEB-TACE procedure and had potential for at least 1 month of follow up, efficacy profile will be analyzed. Accrual will continue during this interim analysis period.

Stopping Rule for Efficacy after 17 patients have completed last planned DEB-TACE

1. If four (4) or fewer responses (complete, partial, or stable disease response according to mRECIST in treated lesion(s) approximately 1 month after last planned DEB-TACE) are observed among first stage of 17 patients.

During the interim efficacy analysis of 17 patients, if four or fewer complete, partial, or stable disease responses are observed in treated lesions by mRECIST on imaging approximately 1 month after last planned DEB-TACE during the first stage, the study will be stopped early; otherwise, additional 34 patients will be accrued. If fourteen or fewer responses are observed by the end of the study, then no further investigation is warranted for DEB-TACE.

Under the study design, if the response rate is <20%, the probability of ending the study during the first stage is 76%. If the response rate is >40%, the probability that the study will be stopped in the first stage is 13%.

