Study Procedure	Doxorubicin Eluting Bead Transarterial Chemoembolization (DEB-TACE): Doxorubicin-loaded LC Beads® are administered via a co-axially placed commercially available hepatic artery catheter into hepatic arteries targeted for treatment. Procedure is performed under direct fluoroscopic visualization until stasis of arterial flow is achieved or until a total of 4 ml of microspheres have been administered, whichever occurs first.

Abstract

Safety Assessments	
• Laboratory tests (Day 1 and Day 7±3 after every DEB-TACE, then 30±7, 90±14, 180±14, 270±14, and 360±14 days after last planned DEB-TACE)• Physical exam/AE assessment (Day 1 and Day 7 after every DEB-TACE, then 30±7, 90±14, 180±14, 270±14, and 360±14 days after last planned DEB-TACE)• MELD score (30±7, 90±14, 180±14, 270±14, and 360±14 days after last planned DEB-TACE))• Imaging procedures to assess tumor burden (30±7, 90±14, 180±14, 270±14, and 360±14 days after last planned DEB-TACE)• Cardiac function monitoring by echocardiography (at baseline and approximately 30 days after last planned DEB-TACE procedure). 
Safety data will be routinely monitored and sequential safety assessments will be conducted as subjects are enrolling to the study. The study will be stopped due to safety/toxicity concern prior to interim efficacy analysis if any of the following 3 stopping rules are met:
 
1. Liver dysfunction (clinical or laboratory [total serum bilirubin], grade 4) that does not improve to baseline or </= grade 3 within 1 month following DEB-TACE in ≥ 7 patients (12% of 51 patients).
OR
2. Renal dysfunction (clinical or laboratory [serum creatinine], grade 3 or 4) that does not improve to baseline or </= grade 2 within 1 month following DEB-TACE in ≥ 2 patients (1.2% of 51 patients).
OR
3. Any grade 5 AE (death) attributed as at least possibly-related to study intervention in ≥ 3 patients (4.8% of 51 patients). 
Stopping Rules for Efficacy after 17 patients have completed last planned DEB-TACE
 
1. If four (4) or fewer responses (complete, partial, or stable disease response according to mRECIST in treated lesion(s) approximately 1 month after last planned DEB-TACE) are observed among first stage of 17 patients.

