Imaging Studies												
Contrast-Enhanced CT or MRI of the abdomen	X											
CT chest with and/or without contrast	X											
Cardiac Function Assessment												
Echocardiogram	X ^{&}					X ^{&}			X ^{&}			X ^{&}
DEB-TACE Procedure												
DEB-TACE**			X			X**			X**			X**
Pharmacokinetics Evaluation												
Pharmacokinetics data acquisition***			X	X	X							

Abbreviation: d = days

* See Table 2 for post-treatment evaluation after DEB-TACE 4. DEB-TACE 3 and 4 are optional for patients with disease extent limited to two liver segments. Patients may proceed to evaluation of response and long-term follow-up after fewer than 4 DEB-TACE treatments at the investigator's discretion.

& Cardiac function will be assessed via echocardiogram at baseline and one month following last planned DEB-TACE.

** Up to 4 DEB-TACE procedures may be performed at approximately 1 month intervals depending upon initial size, number, vascular supply of lesion(s) and interval treatment response on imaging.

*** See plan for pharmacokinetic data acquisition in Sections 8.1 and 8.4

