9.1 Safety

Safety data will be collected as a part of this clinical protocol. The assessments will be based on post-procedure clinical evaluations, laboratory tests, and imaging studies (see section 8 for more details). Six weeks after all 17 patients have been treated with at least one DEB-TACE, data on DEB-TACE safety profile will be analyzed. Final safety analysis will be performed 6 weeks after all 51 patients have been treated with at least one DEB-TACE.

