12.0 STATISTICAL CONSIDERATIONS

12.1 Basis for Sample Size

This is an open label single arm phase II study. The primary objective is to assess the safety and to estimate the objective response rate using mRECIST in treated lesions to the DEB-TACE treatment. The response rate is assumed to be >40% in treated lesions using mRECIST on imaging approximately 1 month after last planned DEB-TACE treatment; the response rate of <20% would be unacceptable for the study treatment. If the response rate is less than a pre-specified minimum goal (i.e. 20%) then the study will be terminated due to inefficacy. Under binomial approximation with 5% type I error and 85% power, a total of 51 patients is required for the study; 17 patients will be accrued in the first stage and 34 patients will be accrued in the second stage.

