12.2 Interim Analysis

After 17 patients have received at least one DEB-TACE and had potential for at least 4 weeks of follow up, the safety profile will be analyzed. The study will be terminated if one of the termination criteria based on unacceptable toxicity listed in section 10.0 has occurred. Final review of the safety will be performed within approximately three months after the treatment of the 17th patient. Stopping rules for lack of safety and efficacy after first stage are defined in Section 10.0. Accrual will continue during these interim analyses.

During the interim efficacy analysis of 17 patients, if four or fewer responses by mRECIST in treated lesions on imaging approximately 1 month after last planned DEB-TACE are observed during the first stage, the study will be stopped early; otherwise, additional 34 patients will be

accrued. If fourteen or fewer responses by mRECIST in treated lesions on imaging approximately 1 month after last planned DEB-TACE are observed by the end of the study, then no further investigation is warranted for the regimen.

Under the study design, if the response rate is <20%, the probability of ending the study during the first stage is 76%. If the response rate is >40%, the probability that the study will be stopped in the first stage is 13%.

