12.3 Analysis Plan

Demographics and Baseline Characteristics

Demographic and baseline laboratory results will be summarized using descriptive statistics.

Safety Analysis

Patients will be monitored for development of recognized complications of DEB-TACE including liver dysfunction, renal dysfunction, ascites, hepatic encephalopathy, hepatorenal syndrome, biliary injury (stricture or leak), cholangitis, cholecystitis, hepatic abscess, abdominal pain, nausea, vomiting, fatigue, and fever. Adverse events will be graded according to NCI CTCAE version 4.03. Prevalence of adverse events will be summarized using descriptive statistics.

Efficacy Analyses

Analyses will be performed using the intent to treat population with exceptions as defined below, which require patient replacement.

Primary efficacy analysis

Primary efficacy will be evaluated as 1-month radiographic response after last DEB-TACE procedure in treated HCC lesions according to 1) RECIST version 1.1 and 2) mRECIST. Patients who do not have any post-baseline tumor assessments will be counted as non-responders. Point estimates of response rate and confidence intervals will be provided.

Secondary efficacy analyses

1. Overall radiographic response by 1) RECIST 1.1 and 2) mRECIST 6 months after the date of the first planned DEB-TACE procedure. This analysis will take into account all measurable hepatic HCC lesions present on cross-sectional imaging 6 months after the date of the first planned DEB-TACE procedure.
2. Time to untreatable progression (TTUP). TTUP is defined as time to disease progression untreatable by liver-directed percutaneous or surgical methods as assessed by treating investigator(s). Patient follow-up up to 1 year after last DEB-TACE will be allowed for this outcome variable.
3. Time to progression (TTP). TTP is defined as the time interval between date of first DEB-TACE procedure and date of imaging documenting development of intra- or extrahepatic disease progression by 1) RECIST 1.1 and 2) mRECIST. Patient follow-up up to 1 year after last DEB-TACE will be allowed for this outcome variable.

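### Section 9.1 can close the final safety analysis before the last patients' adverse-event windows end, and Section 10.2 gives two different triggers for the one futility look

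*Combined protocol and SAP*

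**What the plan says.** **Final safety analysis.** Section 9.1: "Final safety analysis will be performed 6 weeks after all 51 patients have been treated with at least one DEB-TACE". Section 14.3 counts an adverse event as reportable from the start of treatment until 1 month after the last DEB-TACE. Sections 3.2 and 8.3 allow up to four procedures about 1 month apart, and 8.3 allows intervals of up to 90 days. Safety is one of the two primary objectives (Section 2.0).

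**Futility look.** Section 10.2 opens by timing the efficacy analysis "When 17 evaluable patients have been treated with at least one DEB-TACE procedure and had potential for at least 1 month of follow up". A few lines below, the rule is headed "Stopping Rule for Efficacy after 17 patients have completed last planned DEB-TACE", and the abstract has the same condition: "Stopping Rules for Efficacy after 17 patients have completed last planned DEB-TACE". The response itself is read late. Section 12.1 takes it "on imaging approximately 1 month after last planned DEB-TACE treatment", and Section 12.2 stops the study "if four or fewer responses by mRECIST in treated lesions on imaging approximately 1 month after last planned DEB-TACE are observed". Section 12.2 has no efficacy trigger of its own; its one-procedure, four-week trigger belongs to the safety look. Sections 10.2 and 12.2 give early-stopping probabilities of 76% at a 20% response rate and 13% at 40%.

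**Missing scans.** Section 12.3, under the primary efficacy analysis: "Patients who do not have any post-baseline tumor assessments will be counted as non-responders".

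**The concern.** In both places a date is set by the first procedure, although the data needed run from the last. For a patient with one procedure there is no difference. For a patient with two to four there is.

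On safety, the final summary of a primary objective could be closed while some of the last-enrolled patients are still inside their reporting window, or still have sessions to come.

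On futility, two teams following Section 10.2 could take the look on different dates. The look is binding: four or fewer responses stop the study. A look on the opening sentence can come before all 17 responses exist, while the stated operating characteristics assume that all 17 are known.

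**Working it through.** **1. The plan's own figures.** Inputs: 17 patients, stop at 4 or fewer responses, 51 in total, no further investigation at 14 or fewer (Sections 10.2, 12.2); rates 20% and 40% (12.1).

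- Early stop = P(X ≤ 4), X ~ Binomial(17, p): 75.8% at p = 0.20 and 12.6% at p = 0.40. The stated 76% and 13% reproduce.
- Final success = sum over x = 5 to 17 of P(X = x) × P(Y ≥ 15 − x), Y ~ Binomial(34, p): 4.9% at 0.20 and 85.4% at 0.40. The stated 5% and 85% hold.

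**2. Final safety date.** Take 1 month as 30 days. With k procedures g days apart, the 14.3 window closes on day (k − 1)g + 30 after the patient's first session. Section 9.1 cuts at day 42 for the last patient.

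| Procedures (g = 30) | Window closes | Days after the cut |
|---|---|---|
| 1 | day 30 | closed 12 days earlier |
| 2 | day 60 | 18 |
| 3 | day 90 | 48 |
| 4 | day 120 | 78 |

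At the longest permitted interval (g = 90), the gaps for 2, 3 and 4 procedures are 78, 168 and 258 days.

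How many patients this touches is not in the documents. As an illustration, assume one patient per 28.6 days (4 years / 51), 30-day intervals, a share s of multi-session patients between 20% and 49%, and 2, 3 or 4 sessions equally likely among them. At the cut:

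- The last patient is on day 42, so the window is open with probability s.
- The patient before is on day 70.6, open only with 3 or 4 sessions: 2s/3.
- The one before that is on day 99.2, open only with 4 sessions: s/3.
- All earlier patients have closed windows.

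Expected open windows = 2s = 0.4 to 1.0 of 51. Chance of at least one = 1 − (1 − s)(1 − 2s/3)(1 − s/3) = 35% to 71%.

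**3. Futility trigger.** Under the opening sentence, the 17th patient qualifies 30 days after the first session. The scan that counts falls on day (k − 1)g + 30, which is 30, 60 or 90 days later for 2, 3 or 4 monthly sessions. Suppose m of the 17 are mid-course and, as a second condition, are scored as non-responders. Early stop is then P(X ≤ 4) with X ~ Binomial(17 − m, p). Power is computed as in step 1, with the m patients' true responses counted at the end.

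| Counted rate p | m = 0 | m = 1 | m = 2 |
|---|---|---|---|
| 0.40 (false stop) | 12.6% | 16.7% | 21.7% |
| 0.40 (power) | 85.4% | 81.7% | 76.9% |
| 0.50, assumed (false stop) | 2.5% | 3.8% | 5.9% |
| 0.60, assumed (false stop) | 0.3% | 0.5% | 0.9% |

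The last two rows matter because Section 10.2 and the abstract count stable disease as a response, which would push the counted rate above the objective response rate.

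The documents do not give m. Under the assumptions of step 2 it averages 0.6 to 1.5. If the second condition also held, the false-stop chance at a 40% counted rate would be about 15% to 19%.

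**The case against.** **The rule that operates is consistent.** The abstract, the 10.2 rule heading and text, and Section 12.2 all tie the count to the last planned procedure or the scan after it. Only one introductory sentence differs, and accrual continues during the interim analysis, so nothing forces a decision before pending scans arrive. This is fair, and it lowers the severity. The two statements still name different events, and one of them should go.

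**A reader might infer that the plan, as written, raises the false-stop chance above 13%.** The documents do not support that. It requires scans not yet due to be scored as non-response. The only non-responder rule is in Section 12.3 under the primary efficacy analysis, not under the interim analysis. It also covers only patients without any post-baseline scan; the Table 3 footnote refers to "interval treatment response on imaging", so a mid-course patient with such a scan would fall outside it. Without that scoring step, the look is incomplete rather than biased toward stopping. With stable disease counted, the effect is small in any case.

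**A reader might infer that late toxicity would be lost.** It would not. Section 14.3 still collects it, and the continuous monitoring in 10.1.2 and the data safety monitoring committee still see it. The replacement rules in 12.3 use a safety window of 1 month after the first procedure, which 6 weeks does cover. Overall survival is analysed 12 months after the last enrolment, so a complete summary remains possible later. What stands is that the analysis named as final can be incomplete.

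**A reader might also see a conflict between 90-day intervals and the six-month limit on the first follow-up scan, or an unidentified interim population.** Neither holds. Both time limits can bind together, and the Table 3 footnote lets patients go to response evaluation after fewer than four sessions. Section 9.2.4 states who enters the efficacy analysis, and 12.3 states who is replaced.

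**Conclusion.** Two timing defects stand, both minor.

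- Followed literally, Section 9.1 can close the final safety summary 18, 48 or 78 days before the last patient's adverse-event window ends, for 2, 3 or 4 monthly sessions. The gap in days follows from the documents, with 1 month taken as 30 days. The expected 0.4 to 1.0 affected patients of 51 rests on assumed accrual, multi-session share and session mix. The abstract says only that most patients will need one treatment.
- Section 10.2 states two triggers for one binding look, and the earlier one can fall before all 17 responses are known. The 76% and 13% are correct for 17 known responses. The rise to 16.7% or 21.7% is conditional on a scoring step that the documents do not direct and on a counted rate of 40%. It is not a property of the plan as written.

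Sample size, boundaries and the stated error rates are not in question.

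**What to change.** **Section 9.1:** run the final safety analysis once every patient's reporting window under Section 14.3 has closed.

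**Section 10.2:** replace the opening trigger. Take the look when each of the first 17 patients, after any replacement under Section 12.3, has reached the scan date about 1 month after the last planned DEB-TACE or has left the study. Score those who left by the non-responder rule in 12.3, and state that a scan not yet due is not counted as non-response.

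**Leave as they are:** the interim safety look (9.1, 12.2), the continuous safety monitoring (10.1.2), the sample size, the boundaries, and the 76% and 13%.

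**Cost:** wording, plus a delay. At monthly spacing the futility look moves by at most about 90 days (120 − 30), during which about 3 more patients could enrol at the assumed accrual (90 / 28.6 = 3.1). Under the assumptions in the working, the average delay is 19 to 40 days, or about one patient. The final safety analysis moves by at most about 78 days (120 − 42), 14 to 32 days on average. Longer intervals lengthen both: up to 258 days for final safety with four sessions 90 days apart (300 − 42), and up to about 152 days for the futility look if the six-month limit on the first scan is kept (182 − 30).

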At UCSF and other transplant centers, patients with HCC confined to the liver may be offered a spot on the liver transplant list. Expected 5-year survival in patients with HCC who make it to liver transplant is 70-90%, which is better than that for surgery (50%) or liver-directed therapy alone (20-50%) (1). A chief requirement for listing is tumor burden within United Network for Organ Sharing (UNOS) T2 stage (one lesion less than 5 cm or up to 3 lesions each less than 3 cm in size). Patients with UNOS T3 stage (disease confined to the liver without evidence imaging evidence of portal or hepatic vein invasion or extracapsular extension) may also be listed if they undergo successful “down-staging” to UNOS T2 or T1 using liver-directed therapy (7, 8). Liver-directed therapy choices include transarterial chemoembolization (TACE), SIRT, radiofrequency ablation (RFA), and percutaneous ethanol injection (PEI). Typical wait for an organ in UNOS region 5, which includes California, is 1.5-2 years depending on the patient’s blood type. If untreated, HCC is likely to progress during this long waiting period beyond UNOS T2 stage. Therefore, various liver-directed treatment approaches including TACE, RFA, and PEI are

employed to maintain patients active on the transplant list.

TACE is a standard treatment option for patients with intermediate stage, unresectable hepatocellular carcinoma (HCC) without significant hepatic synthetic dysfunction (2). TACE produces an objective tumor response rate of 35%-40% and confers a significant survival advantage as compared to best supportive care (9, 3, 4). Improved quality of life and reduced pain following initiation of chemoembolization are reported among patients undergoing sequential TACE (10). Current indications for TACE include first line treatment for unresectable intermediate stage HCC, as “bridging” therapy to prevent disease progression and drop-out on the liver transplant waiting list, as a method to “down-stage” patients to qualify them for liver transplantation, or enable liver resection through the reduction of disease burden (2, 7).

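### Stable disease counts as a response at the 4/17 futility look, but the sample size rests on the objective response rate

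*Combined protocol and SAP*

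**What the plan says.** Section 12.1 names the design endpoint: "The primary objective is to assess the safety and to estimate the objective response rate using mRECIST in treated lesions". It assumes a rate above 40% and adds that "the response rate of <20% would be unacceptable for the study treatment". From these rates, with 5% type I error and 85% power, it derives 17 + 34 = 51 patients. The Background (1.1) gives 35% to 40% for TACE, also described as an objective response rate.

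Section 10.2 sets the stage 1 rule differently. The study stops "if four or fewer complete, partial, or stable disease responses are observed in treated lesions by mRECIST", and the listed rule just above that sentence defines a response as "complete, partial, or stable disease response according to mRECIST in treated lesion(s) approximately 1 month after last planned DEB-TACE". The Abstract uses the same definition.

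Section 12.2 does not resolve this. It stops the study "if four or fewer responses by mRECIST in treated lesions on imaging approximately 1 month after last planned DEB-TACE are observed" and sets the final rule with "If fourteen or fewer responses by mRECIST in treated lesions on imaging approximately 1 month after last planned DEB-TACE", listing no categories in either case. It also says "Stopping rules for lack of safety and efficacy after first stage are defined in Section 10.0", which sends the reader back to the rule that counts stable disease. The 14/51 sentence in 10.2 and the primary efficacy analysis in 12.3 list no categories. Section 9.2 defines complete response (CR), partial response (PR), stable disease (SD) and progression, but not which of them count as response.

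**The concern.** Objective response ordinarily means CR or PR. Adding SD makes a different and easier endpoint: under the mRECIST definitions in 9.2.3, SD is whatever is neither PR nor progression, so CR+PR+SD takes in every assessed patient who has not progressed in the treated lesions at about one month.

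Two things are at stake. The first is the futility stop, which limits how many patients with marginal hepatic reserve are treated if the regimen does not work. It can lose most of its stated chance of triggering. The second is the final verdict on whether DEB-TACE merits further study. Its error rate depends on whether SD counts at 14/51 and on which endpoint the 20% null describes. With both left open, the choice could be made after the data are seen.

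**Working it through.** **Inputs from the plan.** Null 20%, target 40%, n1 = 17, n2 = 34, N = 51 (12.1); stop at 4 or fewer of 17, negative at 14 or fewer of 51 (10.2, 12.2); stated early stopping 76% and 13% (10.2, 12.2).

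**Assumed.** The documents give no SD rate, so 5%, 10%, 20% and 30% are used. Patients accrued during the interim: none, or 10.

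**Step 1: reproduce the plan.** For a counted endpoint with true rate q:

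- early stop S(q) = P(Bin(17, q) ≤ 4)
- positive conclusion = Σ over x = 5 to 17 of P(Bin(17, q) = x) × P(Bin(34, q) ≥ 15 − x)

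At q = 0.20: S = 0.758, positive = 0.0487. At q = 0.40: S = 0.126, positive = 0.854. These match the stated 76%, 5%, 13% and 85%. The arithmetic of the design is sound for any binary endpoint whose true rates are 20% and 40%.

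**Step 2: count SD at the interim.** Take a true CR+PR rate of p = 0.20, the boundary 12.1 calls unacceptable, and an SD rate s. The interim count then has rate 0.20 + s.

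- Early stop = S(0.20 + s).
- Chance that the same 17 patients have 4 or fewer CR+PR but 5 or more CR+PR+SD = 0.758 − S(0.20 + s).
- Expected N = 17 + k + (34 − k) × (1 − S), with k patients accrued during the interim.

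| SD (assumed) | CR+PR+SD | Early stop | Definitions disagree | Expected N, k = 0 | Expected N, k = 10 |
|---|---|---|---|---|---|
| not counted | – | 75.8% | – | 25.2 | 32.8 |
| 5% | 25% | 57.4% | 18.4% | 31.5 | 37.2 |
| 10% | 30% | 38.9% | 37.0% | 37.8 | 41.7 |
| 20% | 40% | 12.6% | 63.2% | 46.7 | 48.0 |
| 30% | 50% | 2.5% | 73.4% | 50.2 | 50.4 |

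The early-stop chance drops to one half at an SD rate of 6.9%.

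**Step 3: the final conclusion, under each reading of 14/51.**

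*SD at the interim only, CR+PR at the end.* Sum the trinomial probability of x CR+PR and y SD among 17 over all x + y ≥ 5, each multiplied by P(Bin(34, p) ≥ 15 − x).

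*SD at both looks.* Use the Step 1 formula with q = 0.20 + s.

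| SD (assumed) | Interim only: positive at 20% CR+PR | Interim only: positive at 40% CR+PR | Both looks: positive at 20% CR+PR |
|---|---|---|---|
| not counted | 4.9% | 85.4% | 4.9% |
| 5% | 5.8% | 91.0% | 20.2% |
| 10% | 6.4% | 93.8% | 45.4% |
| 20% | 6.9% | 95.5% | 85.4% |
| 30% | 7.0% | 95.6% | 97.5% |

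The interim-only columns are bounded by a design with no early stop: P(Bin(51, 0.20) ≥ 15) = 7.1% and P(Bin(51, 0.40) ≥ 15) = 95.6%.

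*SD at both looks, with the null re-read as a 20% disease-control rate.* The error is 4.9% again, because the counted rate is then 20% by definition.

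**The case against.** The strongest reply is that 10.2 is coherent by itself. It defines responses to include SD, then gives the 14/51 rule, then refers to response rates of 20% and 40%. Read in order, all of these could describe disease control, and the printed probabilities would hold. The word objective appears once in 12.1, the documents never spell it out as CR+PR, and SD is written explicitly three times (Abstract, and twice in 10.2). In a bridging setting, holding tumours stable may be the intended success.

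Much of this is fair. The probabilities do hold for any endpoint with those true rates, and disease control is a defensible choice. But this reading contradicts the endpoint named in 12.1, and nothing justifies 20% and 40% as disease-control rates. Taken literally, a 20% null for CR+PR+SD would put the unacceptable boundary where 80% of patients have progressed in the treated lesions, or are unassessed, at one month; a 40% target would leave 60% in that state. The plan does not argue for either figure.

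Several limits on the size also stand:

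- Every loss in early stopping depends on an assumed SD rate.
- Accrual continues during the interim, which narrows the gap in expected N.
- With SD at the interim only, the error never exceeds 7.1% and power rises.
- The 20% to 97.5% figures require SD at both looks while the null stays at 20% CR+PR.
- Safety stopping is separate from response, and 12.3 reports an estimate with a confidence interval whichever way the decision goes.

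These points moderate the consequence. They do not say which definition governs.

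**Conclusion.** The concern holds, and the point must be fixed before the interim look. The stage 1 rule in 10.2 and the Abstract counts an endpoint that 12.1 did not use for the sample size, and no section settles the conflict.

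The firmest consequence is for the futility stop. At 20% objective response, its stated 76% chance falls below one half once about 7% of patients have SD, and to 13% if 20% do. For the final conclusion, the error ranges from the stated 5%, through at most 7.1% with SD at the interim only, to 20% or more with SD at both looks and a CR+PR null, for SD rates of 5% and above.

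These sizes rest on the assumed SD rates and on objective response having its usual meaning of CR+PR. The contradiction itself rests on neither the SD rates nor the calculations.

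**What to change.** Use one definition of response at both looks, worded identically in the Abstract, 10.2, 12.1, 12.2 and 12.3. The definition that fits the stated sample size is CR or PR by mRECIST in treated lesions, on imaging about one month after the last planned DEB-TACE. With it, 4/17, 14/51, N = 51 and all stated operating characteristics stand. Report CR+PR+SD descriptively as disease control.

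If disease control is the intended decision endpoint, say so, state and justify its null and target rates, and re-derive the sample size, both cut-offs and the early-stopping probabilities.

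The same edit can close three smaller gaps: define evaluable in 10.2, say whether the 12.3 rule that unassessed patients are non-responders applies at the interim, and state that RECIST 1.1 response is reported alongside without driving the decision.

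The first option needs no extra patients, scans or data, only wording changes and the usual protocol review by the PRC and CHR (13.2). Its price is an interim bar harder to pass than 10.2 now reads, and power at the stated 85% rather than the 91% to 96% that SD at the interim only would give under the assumed SD rates. The second option costs a new sample-size justification.
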